## 9.1.11.2 Telemetry

On Day 1 of Part 1 (SRD) and Days 1 and 9 of Part 2 (MRD), cardiac monitoring (telemetry) will be performed for approximately 2 hours prior to dosing through to approximately 12 hours postdose.

The site will use their standard telemetry system for monitoring rhythm and other ECG characteristics from approximately 2 hours prior to dosing through to approximately 12 hours postdose in each period. Subjects should remain sitting or supine for at least 5 minutes before each reading at each PK time point.

The data will be sent to Takeda who will engage a cardiac expert for reading the data, if required. Reporting of this data and any subsequent analysis will be reported separately.

Of interest are the ten (10) second triplicate ECGs that will be extracted at PK time-points for manual reading and precise ECG reading including QT interval measurement. The following parameters will be measured from the subject's ECG trace: heart rate, QT interval, PR interval, QRS interval, RR interval and QTcF and QTcB corrections. The effect of increasing concentrations of TAK-020 on these parameters will be explored.

## 9.1.12 PGx Sample Collection

When sampling of whole blood for PGx analysis occurs, every subject must sign informed consent/be consented in order to participate in the study.

Deoxyribonucleic acid (DNA) and RNA form the basis for the genes that make the body produce proteins such as enzymes, drug transporters or drug targets, and may be evaluated for the genetic contribution how the drug is broken down, or how the drug affects the body. This is called a "PGx research study." Specific purposes of this study include:

- Identifying genetic reasons why certain people respond differently to TAK-020.
- Finding out more information about how TAK-020 works.
- Generating information needed for research, development, and regulatory approval of tests to predict response to TAK-020.
- Identifying variations in genes related to the biological target of TAK-020.

This information may be used, for example, to develop a better understanding of the safety and efficacy of TAK-020 and other study medications, and for improving the efficiency, design and study methods of future research studies.

DNA samples will be used to evaluate drug metabolizing enzymes and transporter polymorphisms that may contribute to the variability in PK of TAK-020. Since PGx is an evolving science, many genes and their functions are not yet fully understood. Future data may suggest a role of these

genes in drug response, which may lead to additional hypothesis-generating exploratory research and diagnostic development on stored samples.

## Part 1- PGx Sample Collection

One whole blood sample (6 mL) for DNA isolation will be collected from each subject in the study before dosing on Day 1, into a plastic potassium ethylenediamine-tetraacetic acid ( $K_2EDTA$ ) spray-coated tube.

Two whole blood samples (2.5 mL per sample) will be collected for RNA analysis from each subject in the study predose on Day 1 and at 24 hours postdose, in a PAXgene tube.

## Part 2 - PGx Sample Collection

One 6-mL whole blood sample for DNA isolation will be collected before dosing on Day 1 from each subject in the study, into plastic K2EDTA spray-coated tubes.

Two whole blood samples (2.5 mL per sample) will be collected before dosing on Days 1, 3, and 9 for RNA isolation from each subject in the study, into a PAXgene tubes.

If necessary and feasible, a second aliquot of blood may be taken if isolation of DNA from the first sample was not successful or possible.

The DNA samples will be used to evaluate common variations in genes which encode drug metabolizing enzymes and transporters. This could be helpful in understanding why there are differences in TAK-020 kinetics between subjects.

Each PGx sample for a study subject should be identifiable on the requisition form with a 7-digit subject ID (the 4-digit site number plus the 3-digit subject number).

The PGx samples will be shipped to Covance at the address listed in Appendix E of this protocol.

The samples will be stored for no longer than 15 years after completion of the TAK-020 study and/or until the drug development of TAK-020 is no longer actively pursued by Takeda or its collaborators. No samples will be stored for longer than permitted by the applicable law and samples will be destroyed upon notification from Takeda. "Stored samples" are defined as samples that are key-coded (the samples are stripped of all personal identifying information but a key links the samples to the clinical data collected from the sample donor) and are used in the analysis of investigational drug or related drugs.

Detailed instructions for the handling and shipping of samples will be compiled in a laboratory manual and provided to the site.

## 9.1.13 PK Sample Collection

## 9.1.13.1 Collection of Plasma for PK Sampling

Blood samples (one 6-mL sample per scheduled time) for pharmacokinetic analysis of TAK-020 will be collected into chilled Vacutainers containing K2EDTA according to the schedule in Appendix A. Instructions for sample processing and shipment are provided in Appendix E.

TAK-020	
Study No. TAK-020-1001	Page 54 of 101
Protocol Incorporating Amendment No. 4.0	27 March 2017

Serial blood samples for determination of TAK-020 will be collected according to Table 9.b. Plasma samples will be taken at the following time points in the first cohort. Based on emerging data in each cohort, the time points may be modified but will not exceed the number of samples presented and will not be taken after 96 hours in the SRD and 48 hours in the MRD.

#### Table 9.b Collection of Blood Samples for PK Analysis

Part 1 (SRD)

Sample Type	Dosing Day	Time Postdose (hours)						
Plasma	1	Predose (within 30 minutes prior to dosing), and at 0.25, 0.5, 0.75, 1, 2, 3, 4, 6, 8, 10,						
		12, 16, 24, 36, 48, 72, and 96 hours postdose						

#### Part 2 (MRD)

Sample Type	Dosing Day	Time Postdose (hours)						
Plasma	1	Predose (within 30 minutes prior to dosing), and at 0.25, 0.5, 0.75, 1, 2, 3, 4, 6, 8, 10, 12, 16, 24, 36, and 48 hours postdose						
Plasma	9	Predose (within 30 minutes prior to dosing), and at 0.25, 0.5, 0.75, 1, 2, 3, 4, 6, 8, 10, 12, 16, and 24 hours postdose						

The actual time of sample collection will be recorded on the source document and eCRF.

Sampling time points may be adjusted based on the preliminary emerging PK data collected from prior cohort(s), but the total number of samples collected per subject should not exceed the planned number.

Placebo samples will not be analyzed by the bioanalytical laboratory except 2 samples per subject receiving placebo, 1 predose and the other around the expected time at which  $C_{max}$  occurred (as emerging from the actual measurement of the samples of the first dose group) to ensure protocol compliance that no additional subjects could have been on active treatment.

#### 9.1.13.2 Collection of Urine for PK Sampling

Serial urine samples for determination of TAK-020 will be collected according to Table 9.c. Urine samples will be taken at the following time points in the first cohort. Based on emerging data in each cohort, the time points may be modified but will not exceed the number of samples presented and will not be taken after 96 hours in the SRD and 48 hours in the MRD.

#### Table 9.cCollection of Urine Samples for PK Analysis

#### Part 1 (SRD)

Sample Type	Dosing Day	Time Postdose (hours)						
Urine	1	Predose (-12-0), and 0-6, 6-12, 12-24, 24-48, 48-72, 72-96 hour postdose intervals						

#### Part 2 (MRD)

Sample Type	Dosing Day	Time Postdose (hours)
Urine	1	Predose (-12-0), and 0-6, 6-12, 12-24 hour postdose intervals
Urine	9	Predose (-12-0), and 0-6, 6-12, 12-24 hour postdose intervals

Instructions for sample processing and shipment are provided in Appendix E.

Urine samples for subjects randomized to placebo will not be analyzed.

## 9.1.13.3 Bioanalytical Methods

Plasma and urine concentrations of TAK-020 will be measured by high-performance liquid chromatography with tandem mass spectrometry.

Part of the archival plasma and urine samples will be sent to TDC Japan/Development Research Center for potential analysis of unknown metabolite characterization, if appropriate.

#### 9.1.14 PK Parameters

The pharmacokinetic parameters of TAK-020 will be determined from the concentration-time profiles for all evaluable subjects. Actual sampling times, rather than scheduled sampling times, will be used in all computations involving sampling times.

CCI

Symbol/Term	Definition						
Plasma/Blood/Serum							
AUC 24	Area under the plasma/blood/serum concentration-time curve from the time 0 to time 24 hours.						
$AUC_{\tau}$	Area under the plasma/blood/serum concentration-time curve during a dosing interval, where tau $(\tau)$ is the length of the dosing interval.						
AUCt	Area under the plasma/blood/serum concentration-time curve from time 0 to time of the last quantifiable concentration						
$AUC_{\infty}$	Area under the plasma/blood/serum concentration-time curve from time 0 to infinity, calculated as $AUC_{\infty}=AUC_t+C_{last}/\lambda_z$						
R	Accumulation ratio (index) calculated as AUC $\tau$ at steady state/AUC $\infty$ after a single dose.						
$R_{ac(AUC)}$	Accumulation ratio (based on AUC), calculated as $AUC_{\tau}$ at steady state/AUC <math>\tau</math> after a single dose.						
C max	Maximum observed plasma/blood/serum concentration.						
C max,ss	Maximum observed steady-state plasma/blood/serum concentration during a dosing interval.						
CL/F	Apparent clearance after extravascular administration, calculated as =Dose/AUC <math>\infty</math> after a single dose and as Dose/AUC <math>\tau</math> after multiple dosing (at steady state).						
$\lambda_z$	Terminal elimination rate constant, calculated as the negative of the slope of the log-linear regression of the natural logarithm concentration-time curve during the terminal phase.						
t 1/2z	Terminal disposition phase half-life, calculated as $ln(2)/\lambda_z$ .						
t lag	Lag time.						
t max	Time of first occurrence of C max .						
V z /F	Apparent volume of distribution during the terminal phase after extravascular administration, calculated as (CL/F)/ $\lambda_z$ .						

The following plasma PK parameters will be determined:

The following urine PK parameters of TAK-020 will be determined:

Urine	
Ae t1-t2	Amount of drug excreted in urine from time 1 to time 2, calculated as $C_{ur} \times V_{ur}$ , where $C_{ur}$ is the concentration of drug excreted in urine and $V_{ur}$ is the volume of urine excreted.
Ae t	Total amount of drug excreted in urine from time 0 to time t.
Ae τ	Amount of drug excreted in urine during a dosing interval $(\tau)$ at steady state.
$f_{e}$	Fraction of drug excreted in urine, calculated as $(Ae_t/dose) \times 100$ . Molecular weight adjustment needed for metabolites.
CL R	Renal clearance, calculated as Ae 0-24 /AUC 24 .

## 9.1.15 PD Sample Collection

Sampling times for sampling collection are shown in the tables below.

Instructions for sample processing and shipment are provided in Appendix E.

9.1.15.2 BTK Occupancy Assay

# 9.1.16 PD Parameters

## 9.1.17 Documentation of Screen Failure

Investigators must account for all subjects who sign informed consent. If the subject is found to be not eligible at this visit, the investigator should complete the eCRF screen failure form.

The primary reason for screen failure is recorded in the eCRF using the following categories:

- PTE/AE.
- Did not meet inclusion criteria or did meet exclusion criteria.
- Significant protocol deviation.
- Lost to follow-up.
- Voluntary withdrawal (specify reason).
- Study termination.
- Other (specify reason).

Subject numbers assigned to subjects who fail screening should not be reused.

## 9.1.18 Documentation of Randomization

Only subjects who meet all of the inclusion criteria and none of the exclusion criteria are eligible for randomization into the treatment phase.

If the subject is found to be not eligible for randomization, the investigator should record the primary reason for failure on the applicable eCRF.

## 9.2 Monitoring Subject Treatment Compliance

Study medication will be administered while subjects are under observation in the clinical research unit. Following administration of the study medication, appropriate mouth and/or hand checks will be performed to ensure that the dose is swallowed and noted in the source document. The date and time of each dose will be recorded in the source documents and on the eCRFs. An inventory of the study medication supplies dispensed will be performed by the site pharmacist or authorized study designee and recorded onto the Drug Accountability Log in the subject's source document records or equivalent. The exact dose time of consecutive subjects may be staggered to facilitate logistics at the site.

## 9.3 Schedule of Observations and Procedures

The schedule for all study-related procedures for all evaluations is shown in Appendix A. Assessments should be completed at the designated visit/time point(s).

## 9.3.1 Final Visit/Check-out

Final Visit for Part 1 will be on Day 5 and Part 2 will be on Day 10. The following procedures will be performed and documented:

- Physical exam.
- Vital signs.
- Weight.
- Concomitant medications.
- Clinical lab tests.
- Serum pregnancy test (female subjects only).

- 12-lead ECG.
- PK blood collection.
- PK urine collection.
- PD blood collection.
- AE assessment.

For all subjects receiving study medication, the investigator must complete the End of Study eCRF page.

## 9.3.2 Early Termination

The reason for discontinuation must be documented in the source document and eCRF. The following procedures will be performed and documented:

- Physical exam.
- Vital signs.
- Weight.
- Concomitant medications.
- Clinical lab tests.
- Serum pregnancy test (female subjects only).
- CCI
- 12-lead ECG.
- PK blood collection.
- PK urine collection.

- PD blood collection.
- AE assessment.

The PK/PD sample collection should be collected at the Early Termination Visit, if possible and relatively close to a protocol-specified time point. For example, collect samples if early withdrawal is due to an AE, and/or if several hours elapsed since last blood draw.

For all subjects receiving study medication, the investigator must complete the End of Study eCRF page.

## 9.3.3 Follow-up Visit/Telephone Call

Subjects with unresolved SAEs, CS laboratory abnormalities, ECG or physical exam findings or at the PI's discretion should be seen for a Follow-up visit on Day 14 ( $\pm 2$  days) in Part 1 for appropriate repeat procedure(s). A Follow-up phone call will be made to all other subjects on Day 14 ( $\pm 2$  days) in Part 1 for an assessment of AEs and concomitant medications. In Part 2, all subjects will return the clinical site on Day 17 ( $\pm 2$  days) for laboratory tests (Hematology, Serum Chemistry, Urinary renal biomarkers, and PD tests), assessment of vital signs, AEs and concomitant medications.

## 9.4 **Biological Sample Retention and Destruction**

In this study, specimens for genome/gene analysis will be collected as described in Section 9.1.12, Pharmacogenomic Sample Collection. The genetic material will be preserved and retained at Covance for up to but not longer than 15 years or as required by applicable law. The sponsor has put into place a system to protect the subjects' personal information to ensure optimal confidentiality and defined standard processes for sample and data collection, storage, analysis, and destruction.

The samples will be sent to a central laboratory that processes the blood sample and serves as a secure storage facility. The samples will be initially stored at Covance. The Sponsor and researchers working with the Sponsor will have access to the samples collected and any test results. All samples collected during the study will be stored securely with limited access and the Sponsor will require anyone who works with the samples to agree to hold the research information and any results in confidence.

The sample will be labeled with a unique sample identifier similar to labeling in the main study but using a code that is different from the code attached to the health information and other clinical test results collected in the study. The sample and data are linked to personal health information with code numbers; the samples are stripped of all personal identifying information but a key linking the samples to clinical analysis data exists. This link means that the subject may be identified but only indirectly. The code numbers will be kept secure by or on behalf of the Sponsor.

Subjects who consented and provided a PGx sample for DNA and RNA analysis can withdraw their consent and request disposal of a stored sample at any time prior to analysis. Notify sponsor of consent withdrawal.

#### 9.5 Blood Volume

Total blood sampling volume for an individual subject is shown in Table 9.d.

					Part 1				
	Sample								
Sample Type	Volume (mL)	Day -28 to -2	Day -1	Day 1	Day 2	Day 3	Day 4	Day 5 (a)	Total Volume (mL)
Safety laboratory samples	29 (b) 19 (c)	1	1	1	1	1		1	124
PK samples	6			13	2	1	1	1	108
PD samples	4			8	2	1	1	1	52
PGx - DNA	6			1					6
PGx - RNA	2.5			2	2				10
Blood volume (mL)		29	19	140	44	29	10	29	300

#### Table 9.dApproximate Blood Volume

(a) If abnormal labs at Check Out are outside markedly abnormal values (to be provided by Takeda in the final study protocol), repeat labs on Day 14 ( $\pm 2$ ) until resolution and report as a TEAE.

(b) Screening Visit only.

(c) Days -1 to 5.

							Par	t 2					
	Sample Number of Samples										Total		
Sample Type	Volume (mL)	e Day 8 to	-2 -2 Day -	-1 Day 1	Day 2	Day 3	Day 4	Day 5	Days 6 to 8	Day 9	Day 10 (a)	Follow- up	Volume (mL)
Safety laboratory samples	29 (b) 19 (c)	1	1	1	1	1		1			1	1	162
PK samples	6			13	2					13	1		174
CCI													
PGx - DNA	6			1									6
PGx - RNA	2.5			2		2				2			15
Blood volume (mL)		29	19	130	37	26	0	19	0	105	29	23	417

(a) If abnormal labs at Check Out are outside markedly abnormal values (to be provided by Takeda in the final study protocol), repeat labs on Day 17 ( $\pm$ 2) until resolution and report as a TEAE.

(b) Screening Visit only.

(c) Days -1 to 10.

The maximum volume of blood at any single day is approximately 140 mL, and the approximate total volume of blood for the study is 300 mL for Part 1 and 417 mL for Part 2.

TAK-020	
Study No. TAK-020-1001	Page 62 of 101
Protocol Incorporating Amendment No. 4.0	27 March 2017

Direct venipuncture is the preferred method of blood collection. Any other method of blood collection will need to be approved by the sponsor before use.

If a catheter with a normal saline flush is used, the total blood volume does not include discarded blood from predraws (assuming approximately 1 mL of blood is discarded each time a sample is collected from a catheter). Should a catheter be used, the total blood volume taken during the study must not exceed 500 mL.

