## 5.2 Endpoints

## **5.2.1 Primary Endpoints**

The primary safety endpoints include the number and percentage of subjects who:

- Experience at least 1 treatment-emergent adverse event (TEAE).
- Meet the Takeda Development Center, Inc. (TDC) markedly abnormal values (MAV) criteria for safety laboratory tests at least once postdose.
- Meet the TDC MAV criteria for vital sign measurements at least once postdose.
- Meet the TDC MAV criteria for safety electrocardiogram (ECG) parameters at least once postdose.

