## Table 9.aClinical Laboratory Tests

aPTT= activated partial thromboplastin time, eGFR= estimated glomerular filtration rate, FSH= follicle-stimulating hormone, hCG=human chorionic gonadotropin, HIV= human immunodeficiency virus, Ig= immunoglobulin, RBC= red blood cells, RNA=ribonucleic acid, WBC= White blood cells.

The local laboratory will perform laboratory tests for hematology, serum chemistries, and urinalysis. The results of laboratory tests will be returned to the investigator, who is responsible for reviewing and filing these results. All laboratory safety data will be transferred electronically to Takeda or designee in the format requested by Takeda. If the laboratory is unable to electronically transfer data, the study site coordinator or designee is responsible for transcribing laboratory results to the eCRF. The investigator will maintain a copy of the laboratory accreditation and the reference ranges for the laboratory used.

Laboratory reports must be signed and dated by the PI or subinvestigator indicating that the report has been reviewed and any abnormalities have been assessed for clinical significance.

All clinically significant laboratory abnormalities must be recorded as a PTE/AE in the subject's source documents and on the appropriate eCRF. A clinically significant laboratory abnormality that has been verified by retesting will be followed until the abnormality returns to an acceptable level or a satisfactory explanation has been obtained.

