## 10.1.3 Additional Points to Consider for PTEs and AEs

An untoward finding generally may:

- Indicate a new diagnosis or unexpected worsening of a pre-existing condition. (Intermittent events for pre-existing conditions underlying disease should not be considered PTEs or AEs.)
- Necessitate therapeutic intervention.
- Require an invasive diagnostic procedure.
- Require discontinuation or a change in dose of study medication or a concomitant medication.
- Be considered unfavorable by the investigator for any reason.
- PTEs/AEs caused by a study procedure (eg, a bruise after blood draw) should be recorded as a PTE/AE.

Diagnoses vs signs and symptoms:

• Each event should be recorded to represent a single diagnosis. Accompanying signs (including abnormal laboratory values or ECG findings) or symptoms should NOT be recorded as additional AEs. If a diagnosis is unknown, sign(s) or symptom(s) should be recorded appropriately as a PTE(s) or as an AE(s).

Laboratory values and ECG findings:

• Changes in laboratory values or ECG parameters are only considered to be PTEs or AEs if they are judged to be clinically significant (ie, if some action or intervention is required or if the investigator judges the change to be beyond the range of normal physiologic fluctuation). A laboratory retest and/or continued monitoring of an abnormal value are not considered an

TAK-020	
Study No. TAK-020-1001	Page 64 of 101
Protocol Incorporating Amendment No. 4.0	27 March 2017

intervention. In addition, repeated or additional noninvasive testing for verification, evaluation or monitoring of an abnormality is not considered an intervention.

• If abnormal laboratory values or ECG findings are the result of pathology for which there is an overall diagnosis (eg, increased creatinine in renal failure), the diagnosis only should be reported appropriately as a PTE or as an AE.

Pre-existing conditions:

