## 10.2.3 Reporting of Abnormal LFTs

If a subject is noted to have ALT or AST elevated >3 ×ULN on 2 consecutive occasions, the abnormality should be recorded as an AE. In addition, an LFT Increases eCRF must be completed providing additional information on relevant recent history, risk factors, clinical signs and symptoms and results of any additional diagnostic tests performed. Concerning ALT/AST increases, please also see Section 6.1.2 Criteria for Stopping Dose Escalation.

If a subject is noted to have ALT or AST >3 ×ULN and total bilirubin >2 ×ULN for which an alternative etiology has not been identified, the event should be recorded as an SAE and reported as per Section 10.2.2. The investigator must contact the Medical Monitor for discussion of the relevant subject details and possible alternative etiologies, such as acute viral hepatitis A or B or other acute liver disease or medical history/concurrent medical conditions. Follow-up laboratory tests as described in Section 9.1.8 must also be performed. In addition, an LFT Increases eCRF must be completed and transmitted with the Takeda SAE form (as per Section 10.2.2).

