# 5.0 ANALYSIS ENDPOINTS

# 5.1 **Primary Endpoints**

The primary safety endpoints include the number and percentage of subjects who:

- Experience at least 1 treatment-emergent adverse event (TEAE).
- Meet the Takeda Development Center (TDC) markedly abnormal values (MAV) criteria for safety laboratory tests at least once postdose.
- Meet the TDC MAV criteria for vital sign measurements at least once postdose.
- Meet the TDC MAV criteria for safety ECG parameters at least once postdose.

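### Table 9.d makes a markedly abnormal Check-out laboratory value a TEAE without clinical judgment, while Section 10.1.3 requires that judgment, so the primary TEAE count rests on two recording rules

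*Protocol*

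**What the plan says.** **The footnote.** Protocol Section 9.5, Table 9.d, footnote (a) is attached to the Check-out column: Day 5 in Part 1 and Day 10 in Part 2. It reads "If abnormal labs at Check Out are outside markedly abnormal values (to be provided by Takeda in the final study protocol), repeat labs", names the follow-up day, and ends "until resolution and report as a TEAE". Apart from the follow-up day, the wording is the same in both parts.

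**The general rule.** Protocol Section 10.1.3 states: "Changes in laboratory values or ECG parameters are only considered to be PTEs or AEs if they are judged to be clinically significant". It gives two routes to clinical significance: some action or intervention is needed, or the investigator judges the change to lie beyond normal physiologic fluctuation. It adds that "A laboratory retest and/or continued monitoring of an abnormal value are not considered an" intervention. Section 9.1.8 agrees: "All clinically significant laboratory abnormalities must be recorded as a PTE/AE".

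**A separate rule for liver enzymes.** Section 10.2.3 covers ALT or AST above 3 × ULN. When this is seen "on 2 consecutive occasions, the abnormality should be recorded as an AE".

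**The endpoints.** Protocol Section 5.2.1 and SAP Section 5.1 list as separate primary endpoints the subjects with at least one TEAE and the subjects who meet the "markedly abnormal values (MAV) criteria for safety laboratory tests at least once postdose". SAP Section 7.11.1 defines a TEAE as any AE in the time window, so it takes over whatever the site recorded.

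**The limits.** The footnote says that the limits will come in the final protocol. The protocol's appendices (A to F) contain no MAV table. The limits are in SAP Appendix B. The protocol amendment is dated 27 March 2017 and the SAP 22 May 2017.

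**The concern.** For a Check-out MAV that the investigator considers not clinically significant, the footnote requires a TEAE and Section 10.1.3 rules one out. The site cannot follow both, and the SAP does not choose between them.

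The rule also depends on the day. The same value is an automatic TEAE at Check-out and a matter of judgment at every other postdose laboratory visit. Because the footnote has no baseline condition, a value that was already markedly abnormal before dosing could be reported as treatment-emergent.

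At stake is the meaning of the first primary endpoint. Under the footnote, one laboratory value scores in both the TEAE and the laboratory MAV endpoint. Under Section 10.1.3 it enters the TEAE endpoint only after clinical judgment. A reporting rule placed in a blood-volume table is easy to miss, so uneven use is plausible.

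**Working it through.** **1. The rules side by side for one postdose MAV**

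| Situation | Table 9.d footnote (a) | Sections 10.1.3 and 9.1.8 | Conflict? |
|---|---|---|---|
| At Check-out, judged clinically significant (either route) | TEAE | AE, hence TEAE | No |
| At Check-out, judged not clinically significant | TEAE | Not an AE | **Yes** |
| Any other postdose visit | Silent | Judgment decides | No, but not the Check-out rule |

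Even in the conflicting row, the primary count (subjects with at least one TEAE) changes only if the subject has no other TEAE.

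ALT and AST show the overlap most clearly, because their MAV limit in SAP Appendix B is also above 3 × ULN. A single such value at Check-out is a TEAE under the footnote and a judgment under Section 10.1.3. It does not by itself meet the two-occasion condition of Section 10.2.3.

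**2. Visits covered** (Protocol Appendix A, footnote (g) of each part)

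- Part 1: postdose laboratory days 2, 3 and 5. The footnote covers 1 of 3.
- Part 2: days 2, 3, 5, 8 and 10 during confinement. The footnote covers 1 of 5. The Day 17 follow-up laboratory tests are a further visit outside the rule.

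**3. Baseline.** Exclusion criterion 18 gives a numeric limit for ALT and AST only (above 1.2 × ULN). Other chemistry and hematology values exclude a subject only if they suggest clinically significant disease. A subject could therefore enter with, for example, triglycerides already above the SAP Appendix B limit of 2.5 × ULN and still have them above it at Check-out.

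**4. Denominators.** The plan's totals reproduce: 9 cohorts × 8 = 72 in Part 1 and 7 × 8 = 56 in Part 2. With 6 active and 2 placebo per cohort:

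- Part 1: 9 × 6 = 54 active and 9 × 2 = 18 placebo.
- Part 2: 7 × 6 = 42 active and 7 × 2 = 14 placebo.

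**5. Effect of one reclassified subject on the TEAE percentage (100/n)**

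| Group | Part 1 | Part 2 |
|---|---|---|
| One dose level | 100/6 = 16.7 points | 100/6 = 16.7 points |
| Pooled placebo | 100/18 = 5.6 points | 100/14 = 7.1 points |
| TAK-020 overall | 100/54 = 1.9 points | 100/42 = 2.4 points |

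**6. How often.** The documents give no rate. Let q be the share of subjects whose only candidate event is a Check-out MAV judged not clinically significant. Take q from 1% to 10% purely as an assumption, the same for all subjects and independent between them.

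- Chance that a given six-subject dose level is affected, 1 − (1 − q)^6: from 1 − 0.99^6 = 5.9% to 1 − 0.90^6 = 46.9%.
- Expected number of subjects affected: 72q = 0.72 to 7.2 in Part 1 and 56q = 0.56 to 5.6 in Part 2.

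**The case against.** **The two rules often agree.** A reader might infer that under Section 10.1.3 a Check-out MAV can count only in the MAV endpoint. The text does not support that. A change judged beyond normal physiologic fluctuation is clinically significant there, and the Appendix B limits are wide (for example potassium below 3.0 or above 6.0 mmol/L, platelets below 75 × 10⁹/L). An investigator could well record many such values as AEs under either rule. This stands, and it confines the conflict to one row of the table above.

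**No bias between arms.** The study is double-blind, has one planned site, and summarizes AEs descriptively. Either rule falls on active and placebo subjects alike. This also stands.

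**The site may have held the limits.** A reader might infer from the empty placeholder that the site could not apply the footnote. The documents do not show what the site held. Sections 5.2.1 and 13.1.5 treat the criteria as existing sponsor criteria, and the SAP's date is not the date of the criteria. What remains is that the protocol's own reference leads nowhere.

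**A specific rule may override a general one.** Section 10.2.3 already adds a specific laboratory rule, and the Check-out restriction has an evident reason: it governs repeat draws after discharge. That explains why repeats are tied to Check-out. It does not explain why AE status should be. Section 10.2.3 sits in the AE section and applies at any visit; the footnote does neither, and Section 10.1.3 makes no exception for it.

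**Planned outputs expose the overlap.** SAP Sections 7.11.1 and 7.11.2 list all AEs, map subjects with TEAEs, and list and map subjects with MAVs. The overlap can be cross-checked, but these outputs do not settle which rule defines the endpoint.

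**Conclusion.** The contradiction is real and narrow. For a Check-out MAV judged not clinically significant, the protocol gives two incompatible instructions, and the SAP carries whichever was followed into a primary endpoint. The count is affected only for a subject with no other TEAE. One such subject is worth 16.7 points in a dose level, but only about 2 points in TAK-020 overall.

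How many such subjects to expect is unknown; the 1% to 10% range is an assumption, not a figure from the plan. The per-subject shifts assume that all planned cohorts are filled and that each has its own dose level. The laboratory MAV endpoint is unaffected under either rule.

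The supported conclusion is that the recording rule is inconsistent across visits. The documents support neither a claim of bias between arms nor a claim that cohorts were in fact handled differently.

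**What to change.** **Reconcile the passages.** In footnote (a) of both halves of Table 9.d, replace the unconditional TEAE instruction with one to report the value as an AE if it meets Section 10.1.3. Leave the repeat-laboratory instruction unchanged. One recording rule then applies at all postdose visits.

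**Fill the placeholder.** Replace the promise of limits in the final protocol with a reference to the sponsor's MAV criteria, as given in SAP Appendix B.

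**Completed cohorts (optional).** Cross-list laboratory-type TEAEs with onset at Check-out in subjects who have a Check-out MAV for the same parameter, and show TEAE incidence with and without them. Label this an approximation: the AE fields in Section 10.2.1.2 do not record why an event was entered, so AEs recorded solely because of the footnote cannot be identified directly.

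**Cost.** Two footnote edits and, if wanted, one cross-listing with a repeated incidence summary. The TEAE percentage may fall slightly. No laboratory information is lost, because the values remain in the MAV endpoint and the listings. Doses for Part 2 Cohorts 5 to 7 are still to be determined in Figure 6.b, so the edit could apply prospectively to those cohorts.
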